5.3. Scheduling

The 12 days of testing will take place after an initial phone call screening. Participants can leave the study at any time for any reason if they wish, without any consequences. The investigator may decide to remove a participant from the study for urgent medical reasons. Participants may be removed from the study if they do not adhere to the study procedure. After elimination, there is no follow-up examination of the participant. In case of withdrawal due to medical complications, the participant is referred to a general practitioner.

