6.4.1 Actlumus wearable light sensor

Participants will wear a light logger around the neck like a pendant to log daily light exposure levels. The light logger is only worn during the day and taken off at night, or when participants get in contact with water (e.g. showering or swimming). We will be using the ActLumus by Condor Instruments, which is an actimeter with integrated light logger. The logger estimates melanopic EDI and photopic lux through several light channels. The logger is very lightweight (12-31 g) and can be clipped to the collar, cloth or worn around the neck or clipped onto glasses to measure light at eye-level. Data will be read locally using a cable and transferred to our computers (no cloud or external server involved) and analysed with a locally installed software from Condor Instruments called ActStudio.

Fig.2. Actlumus wearable light-logger

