6.5 Flowchart and Schedule

After a person expressed interest in participation, researchers will reply by sending the information letter and consent form via email. Subsequently, researchers will schedule a phone call during which they will provide a brief overview of the key aspects of the experiment and address any questions or concerns which participants may have. Additionally, this phone call will serve as an opportunity to evaluate participants' eligibility based on the inclusion and exclusion criteria (see 6.3.1. phone call screening).

Following the phone call and scheduling the participation days, participants will sign the informed consent form during the first visit at the University Hospital.

On day 1, each participant will undergo an eye examination and thereafter starts wearing the wearable sensors and receives instructions on how to complete the smartphone-based self-report forms are provided. After the ambulatory assessment period in participants' everyday life (days 2-10), participants will spend the 11th and 12th day in a controlled office room environment from 08:30 to 17:00 h. Between day 11 and 12, participants will leave controlled conditions from 17:00 h on day 11 to 08:30 h on day 12.

Throughout these 12 days, the sensors continuously record data until they are removed at the end of day 12. Flowchart 1 illustrates this 12-day study period.

[figure not shown]

Fig.6.: Flowchart of chronological events of participants enrolment in the study.

7 Risks

Overall, the study ensures that participants are exposed to conditions within the naturally occurring limits of daily life. We do not expect any risks from participating in the ambulatory assessment with previous research showing high acceptability and no noteworthy reactivity to measurement in participants' behavior. Nevertheless, on day 11 and 12 participants may be exposed to light conditions that could be perceived as uncomfortable compared to their preferences.

Blood pressure measurements will be performed on day 11 and 12 by means of an automatic inflatable cuff. These measurements might feel a bit uncomfortable, but do not induce negative health effects. After wearing the continuous glucose monitor for 12 days, skin irritation can occur from where the sensor wire is inserted.

The eye examinations bring no special risks for participants. Individuals might feel dazzled for a few seconds after the slitlamp examination, especially after retinoscopy.

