8.3 Descriptive statistics

Statistical analysis will be performed using the statistical computer programs SPSS for Mac OS (version 25, IBM) and R Studio for Windows. Descriptive statistics will be reported for all data parameters and will be reported as minimum, maximum, mean, standard deviation (SD) and intraindividual standard deviation (iSD) for data assessed in daily life, and/or standard error of the mean (SEM). As a measure of dispersion, SD will be used for descriptive statistics of the assessed data, while the SEM will additionally be reported for the results of the primary and secondary outcomes.

In case of non-normality, values will either be transformed using log transformation or non-parametric tests will be used. In addition, Pearson correlation coefficients will be computed to correlate parameter values. The unpaired Students t-test will be used to compare outcome measures between the young and old group. Due to the randomized cross-over design, to compare outcomes between the bright and dim office light condition irrespective of age (secondary outcome), a paired t-test will be conducted. Differences will be considered statistically significant when tested two-sided $p < 0.05$. Missing values will not be replaced. We will apply a full information approach using all available data from all participants.

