8.4 Primary and secondary study parameters

As the primary hypothesis of this study is that younger and older individuals differ in their light exposure patterns in everyday life, the primary outcome of this study is melanopic equivalent daylight illuminance (M-EDI) quantified in lux by the Actlumus wearable light sensor. M-EDI may differ between groups with respect to overall daily levels, exposure levels at different times of day (work-day vs. weekend-day), and the difference in exposure levels between work-days and weekend-days. Therefore, M-EDI will be statistically analysed between groups in the following three ways:

1. Compare the area under the curve (AUC) of M-EDI from day 1 to day 8 between young and old (unpaired t-test)

2. Averaging exposure levels over work-days and weekend-days in 1-hour time intervals over 24 hours and compare the two average 24-hour M-EDI patterns between young and old (2-way repeated measures ANOVA, factor 1 (between-subjects) group, factor 2 (within-subjects) time)
3. Averaging the onset of M-EDI in the morning hours and the offset in the evening over work-days and weekend-days and calculate the difference in onset and offset between the averaged work-day and weekend-day between groups (unpaired t-test)

The secondary hypotheses are that light exposure patterns in everyday life are linked to daily metabolic, cardiovascular and psychological outcomes, and that this link is stronger in individuals displaying less degeneration of eye structures.

Accordingly, mixed effects regression analyses will be performed to assess the relationship between different aspects of daily light exposure (momentary M-EDI, average daily exposure level, onset/offset; independent variables) and each of the daily health parameters (metabolic, cardiovascular, psychological functioning, and sleep; dependent variables). To evaluate the role of the degree of eye degeneration, an interaction term between light exposure and eye degeneration will be added to the regression models.

9 Ethics

The study must be approved by the Ethics Committee of RWTH Aachen University. The study is carried out in accordance with the Declaration of Helsinki (the latest version, established in Fortaleza, Brazil, 2013) and the Law on Medical Research involving Human Beings (WMO) and the General Data Protection Regulation (GDPR or GDPR).

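### The first primary analysis uses a fixed-span M-EDI AUC on unreplaced, available data, so read in the ordinary way it mixes light level with recorded time and is biased if retention or wear differs by age group

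*Protocol*

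**What the plan says.** Protocol section 8.4 makes M-EDI from the wearable light sensor the primary outcome and lists three group comparisons. It introduces them with "M-EDI may differ between groups with respect to overall daily levels". The first comparison is "Compare the area under the curve (AUC) of M-EDI from day 1 to day 8 between young and old (unpaired t-test". Nothing in the section divides this AUC by the hours or days recorded. A time-averaged measure does appear in the same section, "average daily exposure level", but only as a predictor in the secondary regressions.

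The general rule on incomplete data, in section 8.3, is: "Missing values will not be replaced. We will apply a full information approach using all available data from all participants".

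Three other places bear on how complete a record will be:

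- Section 5.3: "Participants can leave the study at any time for any reason if they wish, without any consequences". It also lets the investigator remove participants, for instance for non-adherence, with no follow-up afterwards.
- Section 6.4.1: the logger comes off at night and "when participants get in contact with water (e.g. showering or swimming".
- Section 6.5: "Throughout these 12 days, the sensors continuously record data until they are removed at the end of day 12".

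**The concern.** Section 8.4 wants to know whether young and old differ in their daily level of light, which is a rate. The statistic chosen for it is, in the usual sense of the term, a total over a fixed span. M-EDI cannot be negative, so if recording stops early and nothing is filled in, the total can only fall. A short record then looks the same as a dim life.

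Within one group this is only noise. Between groups it matters, because the two age groups may well differ in how long they stay and how steadily they wear the device. The first primary test would then compare light level multiplied by recorded time. It could show an age difference in light that does not exist, or hide one that does.

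**Working it through.** **The protocol's own figure.** Section 6.2 says that 30 per group can detect about d = 0.7 and states no power. At two-sided 0.05, the unpaired t-test with n = 30 per group and d = 0.7 has 76.0% power (77.4% by normal approximation). At an assumed 80% power the detectable d is 0.72 to 0.74. The stated figure is therefore roughly consistent, and the point below does not depend on it.

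**Effect of stopping early.** Section 3 starts recording at about 18:00 on day 1. The span to the end of day 8 is 6 + 7 × 24 = 174 h.

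- Stopping at the end of day 3: (6 + 2 × 24)/174 = 54/174 = 31% of the span.
- Stopping at the end of day 5: (6 + 4 × 24)/174 = 102/174 = 59% of the span.

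Kept in the t-test unfilled, such participants enter with roughly these fractions of the total that they would have had.

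**Effect of a group gap.** If the available-data AUC is the true AUC times coverage, a coverage gap g between groups with identical true light gives a spurious standardised difference of about g/CV. CV is the between-person coefficient of variation, which is assumed because the protocol gives none.

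| Coverage gap | CV 0.3 | CV 0.5 | CV 0.8 |
|---|---|---|---|
| 10 points: spurious d (rejection rate) | 0.33 (25%) | 0.20 (12%) | 0.125 (8%) |
| 20 points: spurious d (rejection rate) | 0.67 (72%) | 0.40 (33%) | 0.25 (16%) |

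**Simulation with no true age difference.** The set-up is 30 per group, lognormal exposure, stopping time uniform over 1/8 to 7/8 of the span (mean fraction 0.5), unworn time counted as zero light, unpaired t-test on the raw scale at two-sided 0.05, and 20,000 runs per scenario. All dropout and wear rates are assumptions. The expected AUC ratio follows by hand:

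- Stopping 0% vs 20%: 1 − 0.20 × 0.5 = 0.90.
- Wear 95% vs 85%: 0.85/0.95 = 0.89.
- Stopping 5% vs 15% with that wear gap: (0.925 × 0.85)/(0.975 × 0.95) = 0.85.

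| Scenario | AUC ratio | False positives, log-SD 0.5 | Log-SD 0.8 |
|---|---|---|---|
| Stopping 0% vs 20% | 0.90 | about 11% | about 7% |
| Wear 95% vs 85% | 0.89 | about 13% | about 7% |
| Stopping 5% vs 15% plus wear 95% vs 85% | 0.85 | about 20% | about 10% |
| Stopping 0% vs 5%, 5% vs 10%, 0% vs 10% | 0.95 to 0.98 | about 5 to 6% | about 5% |
| Equal stopping and wear | 1.00 | about 5% | about 5% |

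**Masking.** Take CV 0.5 in both groups and a true difference of 0.7 SD in favour of the older group. If the older group has 85% wear and 10% leavers against 95% and none, power falls from about 63% to 18%.

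**Off-body time depends on handling.** Take a constant 200 lux over 16 waking hours, which is 3200 lux·h. A 3 h gap scored as zero or dropped gives 2600 lux·h. Bridging the gap by the trapezoidal rule gives 3200. A logger left recording off the body stores ambient light, which may be above or below the wearer's exposure.

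**After normalisation.** Dividing by recorded time brings the rejection rate back to about 5% in every no-difference scenario, provided that missing time is unrelated to light level.

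**The case against.** The best defence is that the protocol leaves the scoring open. It does not call the AUC a total, does not say how gaps are integrated, and speaks of daily levels, which fits a per-day AUC. Scoring unrecorded days as no light amounts to filling them with zero, which section 8.3 could be said to forbid, and its full-information sentence may have the mixed models in mind. This stands in part: summation is the ordinary meaning of the term, not the protocol's own word. But the alternatives do not fit the text well either. Dropping incomplete records conflicts with using all available data from all participants, and bridging gaps sits badly with not replacing missing values.

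Four stronger readings are tempting and are not supported:

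- A reader might infer that taking the logger off always lowers the AUC. It does not: the direction depends on gap handling and ambient light. The sentence in section 6.5 is general and does not say that unworn readings count as exposure.
- A reader might infer that the test is biased as planned. Bias needs coverage to differ by age group, and the protocol gives no rates to show that it will. Section 12 ties payment to completing the study, and leaving after day 8 cannot affect this AUC.
- A reader might take 20% as the expected false-positive rate. It is the upper end of the dropout and wear scenarios simulated at log-SD 0.5 and 0.8.
- A reader might count the lack of wear thresholds as an error. Such detail commonly belongs in a SAP, which is not at hand.

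It also stands that the second primary analysis averages hourly levels over days and so does not shrink mechanically with missing days. The primary hypothesis does not rest on the AUC alone.

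**Conclusion.** The point holds in a limited form. Sections 8.3 and 8.4 together fix a fixed-span AUC, no replacement, and inclusion of all participants' available data. Under the ordinary reading, a partial record gives a smaller value for reasons unrelated to daily light level. This is a mismatch between the stated target and the chosen statistic, not merely a detail left for later.

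Its size is conditional. The effect on an early leaver is certain if the partial record stays in. The effect of off-body time has no fixed direction. Group bias arises only if retention or valid wear differs by age group. The figures rest on assumed dropout, wear and spread: little harm for dropout gaps of 5 to 10 points, and false positives of about 10 to 20% when moderate gaps in both dropout and wear coincide. A time-normalised measure is better suited to the stated target and cheap to adopt, so the change is advisable.

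**What to change.** In section 8.4, define analysis 1 as average daily M-EDI exposure over the chosen window: each participant's AUC over waking hours per valid recorded day. State that:

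- off-body periods are flagged from the logger's own actimetry and set to missing, not read as exposure;
- participants who left early are included if they have enough valid days, with the thresholds fixed before analysis, in the SAP if preferred;
- the partial first day is not counted as a full day;
- valid days and wear time are reported by age group.

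This needs a change of wording and one processing step on data already collected, with no new visits or measurements. There are two costs. Participants with too few valid days do not contribute to analysis 1. The average also assumes that missing time is unrelated to light level, which the wear report by group helps readers to judge but cannot prove.

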This study is designed as an observatory field study of characterizing younger and older adults' everyday life in terms of light exposure patterns as well as cardiovascular, metabolic and psychological health parameters over 10 days continuously through wearables and smartphone-based self-reports (ambulatory assessment period). On the first day of data collection, each participant will undergo an eye examination at the Institute of Ophthalmology. Thereafter participants start wearing the wearable sensors and instructions on how to complete the smartphone-based self-report forms are provided. Data will be collected from the first evening onwards (ca. 18:00 h). After the ambulatory assessment period under free-living conditions, participants will spend the 11th and 12th day in a controlled office room environment from 08:30 to 17:00 h. In a randomized cross-over design, the 11th and 12th day will be spent in either bright (1250 lux) or dim office lighting (10 lux). On these days, participants will continue to wear the wearables and complete the same smartphone-based self-reports as over the 10-day ambulatory assessment period. Between day 11 and 12, participants will leave controlled conditions from 17:00 h on day 11 to 08:30 h on day 12. On day 11 and 12, participants will receive a standardized fluid meal for breakfast and a bread-based meal for lunch, and are otherwise instructed to avoid any food, caloric or caffeinated beverages between 08:30 and 17:00 h. After removing all wearables on day 12, the study ends at 17:30 h. Over these 12 days of data collection, participants will be asked to keep their bedtimes at home as consistent as possible between days, and on day 11 and 12 they will be instructed to come to the office facilities fasted without any caloric intake after 22:00 h on the previous evening of day 10 and 11, respectively.

To minimize the burden on participants in this study, we use mobile and user-friendly devices for data collection and give clear instructions for data collection. We keep individual assessments short, limit the study duration to 12 days and provide incentives for participation (up to €200 reimbursement). On day 11 and 12, participants are mostly free to do whatever they like to do while being in the office environment (e.g. watching movies, paperwork, reading, video-meetings etc.).

[figure not shown]

Fig.1. Overview of study design.

4. Responsibilities

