6.4 Measurement devices

All measurements within the framework of the research project are non-invasive, except for placing a continuous glucose monitor on the non-dominant forearm of participants from day 1 of the data collection period onwards.

Table 3 shows the different types and respective resolutions of the recorded data.

The continuous glucose monitor and the light sensor will be worn throughout the 12 days of the study, while the thermal skin sensors and the ambulatory blood pressure device will only be worn on day 11 and 12, between 08:30 and 17:00 h respectively.

Table 3. Data collected, methods and resolution.

Data	Unit	Device name	Frequency
Skin temperature	°C	iButtons	1 min
Interstitial glucose	mmol/L	Abbott Freestyle Pro IQ	15 min
Illuminance	Lux Melanopic EDI	Actlumus	1 min
Blood pressure	mmHg	ECGpro Holter-RR USB	15 min

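### The first primary M-EDI analysis sums an evening-only day 1 and leaves recorded free-living days 9 and 10 unused; a weighted daily mean over days 2-10 is a cheap improvement

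*Protocol*

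**What the plan says.** - **Analysis window.** Section 8.4 lists three primary analyses of M-EDI. The first is: "Compare the area under the curve (AUC) of M-EDI from day 1 to day 8 between young and old (unpaired t-test". Its stated purpose is to compare the general daily level of exposure between the age groups. The second analysis (hourly profiles) and the third (onset and offset) name no day window.
- **Recording period.** Section 3 describes free-living measurement "over 10 days continuously through wearables and smartphone-based self-reports (ambulatory assessment period" and adds: "Data will be collected from the first evening onwards (ca. 18:00 h". Section 6.5 gives the free-living stretch as "everyday life (days 2-10", with controlled office lighting on days 11 and 12.
- **Device.** Section 6.4 states: "The continuous glucose monitor and the light sensor will be worn throughout the 12 days of the study". Section 6.4.1 adds: "The light logger is only worn during the day and taken off at night".
- **Reason for stopping at day 8.** None is given.

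**The concern.** The window is awkward at both ends.

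**Start.** Day 1 is the eye-examination day. It supplies only an evening, and the start time is approximate. A total AUC grows with the length of the recorded stretch, so a start that varies between participants adds variation unrelated to anyone's habitual exposure. One evening plus seven days is also hard to read as a daily level.

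**End.** Days 9 and 10 are free-living, are recorded on the same device and fall before the office days. They are paid for in participant burden and then not used in this analysis.

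What is at stake is precision and readability of one primary comparison, in a study of 30 per group that states a detectable effect of about d = 0.7 and no power.

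**Working it through.** **1. Coverage (clock hours, ignoring night removal)**

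Inputs: start at about 18:00 on day 1 (section 3), free-living to the end of day 10 (section 6.5), window of days 1 to 8 (section 8.4).

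- Window: 6 + 7 × 24 = 174 h.
- Recorded free-living period: 6 + 9 × 24 = 222 h.
- Unused: 222 − 174 = 48 h, and 48/222 = 21.6%. This is 2 of 9 full days.
- Share of day 1 covered: 6/24 = 25%, evening only.

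**2. Balance of the week**

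Counting over all seven possible weekdays for day 1:

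- Days 2-8 always hold 5 weekdays and 2 weekend days.
- Days 2-10 hold 2, 3 or 4 weekend days.

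A plain nine-day mean would therefore mix weekdays and weekend days differently between participants. Weighting the two averages 5:2 removes this.

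**3. Effective number of days under 5:2 weighting**

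With w weekdays and e weekend days, and equal within-person variance per day:

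effective days = 1 / [(5/7)²/w + (2/7)²/e]

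| w, e | Sum in brackets | Effective days |
|---|---|---|
| 7, 2 | 0.0729 + 0.0408 = 0.1137 | 8.8 |
| 6, 3 | 0.0850 + 0.0272 = 0.1122 | 8.9 |
| 5, 4 | 0.1020 + 0.0204 = 0.1224 | 8.2 |
| 5, 2 (days 2-8) | 0.1020 + 0.0408 = 0.1429 | 7.0 |

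**4. Effect on the standard error**

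Variance of a person's mean over k effective days, in units of the total single-day variance: ICC + (1 − ICC)/k. The protocol gives no ICC, so a range is assumed. The SE ratio is the square root of the variance ratio.

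| Assumed ICC | k = 7 | k = 8.2 | k = 8.9 | SE reduction |
|---|---|---|---|---|
| 0.15 | 0.2714 | 0.2537 | 0.2455 | 3.3 to 4.9% |
| 0.30 | 0.4000 | 0.3854 | 0.3787 | 1.8 to 2.7% |
| 0.50 | 0.5714 | 0.5610 | 0.5562 | 0.9 to 1.3% |
| 0.70 | 0.7429 | 0.7366 | 0.7337 | 0.4 to 0.6% |

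Example, ICC 0.15 and k = 8.2: 0.15 + 0.85/8.2 = 0.2537; 0.2537/0.2714 = 0.9345; √0.9345 = 0.967, a reduction of 3.3%.

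**5. What that means for power**

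Section 6.2 gives n = 30 per group and d of about 0.7, with no power figure to reproduce. An unpaired t-test at two-sided 0.05 has 76.0% power with those inputs. Suppose d = 0.7 refers to a seven-day mean, which section 6.2 does not say. Dividing 0.7 by the SE ratio then gives power of 78.8 to 80.0% at ICC 0.15 and 76.3 to 76.5% at ICC 0.7.

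The comparison in steps 3 to 5 is with the seven full days in the stated window. The noise from the variable start on day 1 is not quantified, because the protocol gives no spread of start times.

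**The case against.** **A fixed window inside the recorded period is not an error in itself.** This is right. Sections 3, 6.4 and 6.5 say what is recorded, and section 8.4 says what one analysis uses. The two are compatible, so the point is a better choice of window.

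**A one-week window may have been intended.** Read from 18:00 on day 1 to 18:00 on day 8, it would be 7 × 24 = 168 h, and days 2-8 are exactly one calendar week. That balance is a real merit and is why the 5:2 weighting is needed. But the text states no clock times and no such intent. If day 1 meant the first full day, that would disagree with the day numbering in sections 3 and 6.5 and would still leave day 10 out.

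**Stronger readings that the protocol does not support:**

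- *That the window breaks the promise in section 8.3 to use all available data.* That sentence follows the statement that missing values are not replaced. It is a missing-data rule and does not commit every analysis to every recorded day.
- *That the age comparison is biased.* The part-day applies to both groups by design. Bias would need start times or evening exposure on day 1 to distort the groups differently, and nothing in the protocol shows that.
- *That days 9 and 10 are lost to the primary outcome as a whole.* Only the first of the three analyses names days 1 to 8.

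**The gain is small and rests on an assumed ICC.** This stands. At an ICC of 0.5 or more, the reduction in standard error is below 1.5%.

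**Conclusion.** The point holds as a modest, low-cost improvement. As written, the first primary analysis adds one evening of uncertain length to seven full days, which is not a daily level, and it uses 7 of 9 full free-living days. The consequence is start-time noise of unknown size and a standard error that could be about 0.4 to 4.9% smaller, over assumed ICCs of 0.7 down to 0.15. These figures assume equal within-person variance on weekdays and weekend days, independent day-to-day deviations, and complete days. The finding does not show bias in the age comparison or a conflict with section 8.3.

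**What to change.** Replace the first analysis in section 8.4 with wording to this effect: *For each participant, the AUC of M-EDI is computed for each full free-living day (days 2 to 10). Daily values are averaged separately over weekdays and weekend days, and the two averages are combined with weights 5/7 and 2/7. The result is compared between age groups with an unpaired t-test. Day 1 is excluded. The same measure over days 2 to 8 is reported as a sensitivity analysis.*

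This keeps the AUC and the planned test, removes the part-day, holds the weekly mix constant and uses data already collected. Scaling by valid recorded hours is a separate question: with a logger worn only by day, it would change what is estimated, and it is not needed here.

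The cost is a short text change and a slightly more complex summary measure. The weighting gives back a little of the gain, from 9 days to 8.2 to 8.9 effective days.

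### The everyday-life mixed models in section 8.4 list no work-day/free-day term, so the light slope can pick up a weekend effect

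*Protocol*

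**What the plan says.** Protocol section 8.4 states the secondary hypotheses: "light exposure patterns in everyday life are linked to daily metabolic, cardiovascular and psychological outcomes", and this link is stronger where the eye structures are less degenerated. For these, "mixed effects regression analyses will be performed to assess the relationship between different aspects of daily light exposure" and each daily health parameter. The predictors are given as "momentary M-EDI, average daily exposure level, onset/offset; independent variables". The outcomes are metabolic, cardiovascular, psychological and sleep parameters. One further term is named: "an interaction term between light exposure and eye degeneration will be added to the regression models". No covariate is mentioned, and no other document is cited for one.

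The same section uses day type for the primary outcome. It says that M-EDI may differ between the age groups in, among other things, "the difference in exposure levels between work-days and weekend-days". Primary analysis 2 averages light over work-days and weekend-days, and primary analysis 3 contrasts light onset and offset between them.

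**The concern.** Day type is a plausible common cause. A free day can change rising time and time outdoors, and so light. It can also change stressors, leisure, sleep and meal timing, and so mood, vitality, sleep and glucose. Light does not cause day type. Because it varies within a person, a random person intercept leaves it in the slope. Because it acts between days, a time-of-day term would not remove it either.

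Light onset and offset, which primary analysis 3 contrasts by day type, are also predictors in the secondary models, where that contrast does not appear. At stake is the first secondary hypothesis: a weekend effect alone could produce an apparent light-health link. If weekend shifts also differ by age, the same mechanism can reach the eye-degeneration interaction, since degeneration is expected to differ between the age groups (section 6.2).

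**Working it through.** The protocol gives no figure of its own to reproduce here. Its sample-size statement (30 per group, d about 0.7) concerns the young-versus-old comparison.

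**Inputs from the protocol.** 60 participants (section 5); days 2-10 in everyday life, taken as 9 full days (section 6.5); two-sided 0.05 (section 8.3).

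**Assumptions.** The true light effect is zero. The weekend shifts light by *a* and the outcome by *b*, in within-person SD units. The protocol gives neither, so a range is shown. Start weekdays are evenly spread, and the regression is within-person.

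**Step 1: within-person variance of day type.** With *k* weekend days out of 9, the sum of squares is k(9−k)/9, which is 14/9, 18/9 and 20/9 for k = 2, 3 and 4. Over the seven start weekdays these occur 4, 2 and 1 times. The mean is (4×14 + 2×18 + 20)/(7×9) = 112/63 = 1.778. Divided by 8 degrees of freedom, q = 0.222.

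**Step 2: bias and test, no day-type term.**
- Bias = abq/(1 + a²q).
- Residual variance s² = 1 + b²q − bias²(1 + a²q).
- SE = √[s²/(480(1 + a²q))], with 480 = 60×8.

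At 0.5/0.5: bias = 0.0556/1.0556 = 0.053; s² = 1.053; SE = 0.0456; ratio 1.15; rejection probability 21%.

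At 0.8/0.5: bias = 0.0889/1.142 = 0.078; s² = 1.049; SE = 0.0437; ratio 1.78; rejection probability 43%.

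**Step 3: simulation (60 × 9 days, same shift for everyone, 2,000 runs without and 1,000 with the term).**

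| Shift in light / outcome | Mean bias | False positives, no term | With day type |
|---|---|---|---|
| 0 / 0.8 | −0.001 | 5% | 5% |
| 0.2 / 0.2 | 0.008 | 5% | 4% |
| 0.3 / 0.3 | 0.020 | 7% | 4% |
| 0.5 / 0.3 | 0.031 | 11% | 4% |
| 0.5 / 0.5 | 0.053 | 21% | 5% |
| 0.8 / 0.5 | 0.078 | 44% | 5% |
| 0.8 / 0.8 | 0.126 | 80% | 4% |

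Repeat runs gave 7-8% at 0.3/0.3, 21-22% at 0.5/0.5 and 42-44% at 0.8/0.5. A random-intercept mixed model (250 runs) gave 18% and 41% at 0.5/0.5 and 0.8/0.5 without the term, and 8% and 5% with it.

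**Step 4: shifts that differ by age group.** Take the extreme case of a shift in the 30 young participants only.
- Without a term, the light slope rejects in 15% of runs at 0.8/0.5 and 58% at 1.0/1.0.
- A single day-type term fits the average shift. It leaves +a/2, +b/2 in the young and −a/2, −b/2 in the old, and the products have the same sign. The remaining bias is (a/2)(b/2)q/(1 + a²q/4). At 1.0/1.0 this is 0.0556/1.0556 = 0.053, the same as 0.5/0.5 in Step 2, so about 21%. At 0.8/0.5 it is 0.0222/1.036 = 0.021, about 8%. Simulation gave 19-21% and 8-9%.
- The light by degeneration test stays near 5% when shifts are equal. With degeneration tracking age, it is 12% for young 0.8/0.5 and old 0.2/0.1, and 21% for young 0.8/0.8 and old 0/0, without a term. With shifts in the young only and a single day-type term, it is still 6-16%.
- Adding day type by age group returns both tests to about 5%.

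**The case against.** The strongest objection is that this rests on silence. Section 8.4 names exposures, outcomes and one interaction, and no covariates at all. It does not say that the models contain only these terms. A covariate list for a secondary model is commonly left to the statistical analysis plan, which is not at hand and may include day type. That stands as a limit: the final models cannot be said to omit it. But section 8.4 goes beyond naming a model class. It lists the predictors and the added term and refers to no other place, so an analyst who follows it fits the confounded model.

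Several stronger readings are tempting but not supported:

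- **That the protocol expects light to differ by day type.** It says only that the work-day/weekend difference may differ between groups, and analysis 2 does not presuppose a day-type difference.
- **That weekend effects will be read as light effects.** With shifts of 0.2-0.3 SD there is almost no inflation, and with no shift in light there is none.
- **That eating is an affected outcome.** It is not among the listed dependent variables and could matter only through glucose.
- **That the interaction test is always inflated.** It is not when the age groups shift alike.
- **That everyday blood pressure is affected.** Section 6.4 restricts blood pressure measurement to days 11 and 12.

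The wording of the hypothesis as a link softens the matter but does not settle it, because section 7 presents the results as a basis for suggesting changes in light exposure behaviour.

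**Conclusion.** The point holds in a conditional form. As listed in section 8.4, the everyday-life models leave day type free to confound the within-person light slope. The direction of the problem is clear; its size is not known. False-positive rates run from about 5-8% for shifts up to 0.3 SD in both light and outcome, to about 21% at 0.5/0.5 and 43% at 0.8/0.5. These figures assume one common weekend shift, Saturday and Sunday as free days, independent errors and no true light effect. If only the young shift, inflation of the light slope is smaller, but the interaction test then becomes vulnerable and a single day-type term is not enough. The concern is confined to secondary, observational analyses. The primary young-versus-old comparison of light is untouched.

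**What to change.** In section 8.4, state that every everyday-life mixed model, including those with the light by eye-degeneration interaction, contains day type (work-day versus free day) and day type by age group as fixed effects. Define day type from the Activity item in Table 2, or from the calendar for participants without work-days.

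This takes one or two sentences and uses data already collected. The price is a slightly larger standard error for the light slope. Where day type has no effect on the outcome, the factor is about √(1 + a²q): √1.056 = 1.03 for a light shift of 0.5 SD and √1.142 = 1.07 for 0.8 SD. Where day type does affect the outcome, the smaller residual variance offsets part of this. A study-day term is not needed for this purpose.
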